NCT04261985 Unique Protocol ID: 1R21HD096298-01A1

Secondary IDs: 1R21HD096298-01A1

A Mobile Phone Based Pilot Intervention to Prevent Obesity in Latino Preschool Children

February 17, 2022

Title: A mobile phone pilot intervention to prevent obesity in Latino preschool children

Conditions:

Childhood obesity interventions
Mobile Health
Latino populations

Eligibility Criteria:

Eligibility criteria will include an adult female or male caregiver who(1) self-identifies as an individual of Latino descent; (2) has a 2- to 5-year-old child/grandchild (where the relationship does not have to be biological but caregiver is a legal guardian); (3) lives with child or grandchild or cares for child/grandchild at least 20 hours per week; speaks Spanish or English; (4) is fluent in English or Spanish; (5) owns a mobile smart phone; (6) is able and willing to receive and interact with text messages on parenting, dietary, and physical activity strategies for young children (focus group Aim1); **or** (7) has the ability and willingness to participate in a 4-week mHealth intervention (Specific Aim2) and complete baseline, 1-month, and 6-month post-baseline measurement protocols. The ability to participate will be determined by using of a Subject Comprehension and Participation Assessment Tool. Families will be excluded if the child has a failure to thrive diagnosis or medical conditions related to overweight status such as Prader-Willi Syndrome.

Age Limit:

Minimum age 2 yrs
Maximum no limit (N/A)

PROTOCOL SYNOPSIS

Summary

The study objective is to pilot a stand-alone 4-week mobile phone intervention with Latino mothers, fathers, and grandparents, geared at building caregiver strategies to support evidence-based and age appropriate dietary, media-viewing, and physical activity practices among 2- to 5-year old children in order to resolve key challenges of traditional in-person pediatric obesity interventions (e.g. transportation, time), and also leverage important determinants of Latino health (e.g. familism, language). The primary and secondary endpoints are reached when all family cohorts complete their 6-month post-baseline data collection procedures. The study population is biological or adoptive mothers, fathers, and grandmothers of 2-to-5-year old Latino children living in Los Angeles, California without failure to thrive diagnosis or medical complications associated with their weight status such as Prader-Willi Syndrome

A prospective randomized pilot study will be completed to assess acceptability, feasibility, and preliminary effect sizes on children's weight-related behaviors and BMI z-scores at 6 months post-intervention, in preparation for a larger randomized trial to evaluate the intervention's efficacy. The intervention will deliver 4 interactive texts every week for one month to Latino caregivers of 2 to 5-year old children and 2-months of mobile phone "booster" doses that incorporate behavioral change techniques using a group strategy, a cornerstone of many effective in-person parent-focused pediatric obesity interventions. The study will first use qualitative methods to maximize the acceptability and usability of the existing mobile phone group learning strategies with a small group of Latino mothers, fathers, and grandparents. A 4-week mobile phone pilot intervention will then be completed with 66 caregiver-child dyads recruited from two WIC sites in East Los Angeles. Eligible caregiver-child dyads will be randomly assigned into the 4-week mobile phone intervention condition or the comparison condition, in which caregivers receive usual WIC services. Acceptability and feasibility outcomes will include: (1) the number of families needed to be screened per month; (2) attrition rates of a randomized mobile phone intervention with Latino populations; (3) dose and exposure of texts; (4) frequency of sharing/replying to texts by caregiver-type; (5) number of completed baseline and follow-up data; and (6) family-centeredness of the intervention. Pre- and post- intervention data will be collected at baseline, 1-month, and 6-months after the intervention begins in order to estimate preliminary effect sizes and standard deviations associated with child dietary, physical activity, and media viewing practices and BMI scores. Mediators of the intervention will include measures of caregiver self-efficacy, caregiver feeding practices, and group support. The pilot study will provide the acceptability, feasibility, and preliminary data on child weigh-

related behaviors and BMI to develop an R01 proposal to test the intervention's effectiveness via a large randomized controlled trial.

Recruitment and Retention

The proposed research studies will include focus groups to maximize acceptability and usability of a 4-week childhood obesity mHealth intervention, followed by a pilot intervention research study to assess feasibility and preliminary outcomes of the 4-week mHealth intervention. The intervention's focus on weight-related behaviors during early childhood, requires the involvement and participation of child caregivers as the agents of change for child weight-related behaviors. The proposed research activities will, therefore, target mothers, fathers, grandmothers, and young children (2-5 years old).

Study participants (mothers, fathers, and grandmothers) will be recruited using recruitment fliers and learn about the study by making contact with study investigators. All participants will provide written informed consent to participate in the study. To ensure that potential participants understand the study and the activities he/she will be asked to complete, we will use a Subject Comprehension and Participation Assessment Tool to assist in this process. Children's assent or consent will not be obtained due to their young age (2-5 years old), although they may opt out. During consent procedures, participants will be given both written and verbal (in Spanish and English) information about the study to address low-literacy levels or limited English proficiency. Only legal guardians of a child will provide consent for the study, and non-legal guardians will be excluded. Participants will be told and given information relating to all the potential risks of study involvement, including the potential for loss of privacy and the ethical obligation of researchers to report observed neglectful or abusive behaviors. All protocols for recruitment and informed consent will be vetted with our community partner, WIC, and included in our UCLA IRB application.

Bilingual and bi-cultural research assistants will be trained and supervised by the research team (PI and Co-Is) and will be responsible for recruiting, screening, and consenting potential participants. We will propose distributing recruitment flyers explaining the study as families visit WIC centers. These recruitment flyers will be made available in English and Spanish and written at a 6th-grade reading level to ensure the information about the research activities are clear and understandable. A mother, father, or grandmother who cares for a child who is between the ages of 2 – 5 years old who expresses an interest in the study, will be instructed in the flyer to contact project staff, who will explain the study and invite the families to participate in the study. If introductory letters are not found to be effective for recruitment, we will recruit potential participants in person.

For the focus group study (Specific Aim1) each caregiver, will be asked to complete one focus group session. Monetary incentives for participation will be comparable to amounts used in other research activities in the community, a \$25 gift certificate for focus group participation. For the mHealth pilot intervention activities, mothers, fathers, and grandmothers will be asked to participate in a 4-week mobile phone intervention to build caregiver knowledge and skills related to healthy weight-behaviors for young children (Specific Aim 2). We will use similar recruiting strategies used for Specific Aim1 where potential parents will be recruited from community centers. Recruitment strategies will have a goal of enrolling equal numbers of mothers, fathers, and grandmothers. If recruitment flyers to encourage study participation do not yield the number of required participants, we may recruit participants' in-person at WIC centers waiting rooms. Monetary incentives for all data collection points will be provided to retain participants in the study. We will use amounts comparable to other research activities in the community, a \$25 gift card for each data collection point. In addition, if follow-up measurement appointments at the 6-month data collection points are low we may also explore a higher incentive amount to minimize attrition (\$35).

DATA and SAFETY MONITORING PLAN

Data Safeguarding

The qualitative and quantitative research methods of the proposed studies will not involve the collection of biological samples or the use of drugs. The data collection activities of the proposed studies all constitute minimal-risk procedures. As such, there is no need to convene a formal data safety monitoring board but the study will include a Safety Officer. The PI, [name], and the Safety Officer will have ultimate responsibility for data safeguarding. [name] will be responsible for day-to-day oversight of the data collection and data management, training the data collection team in data safeguarding techniques, and oversight of all staff who handle participant-identifying computer files, surveys, tracking forms, and other identifiable data. All research assistants and staff involved in data collection or handling of data, will receive training that addresses data safeguarding and confidentiality, and will sign confidentiality agreements. Raw data in need of safeguarding

will include files generated to link identifying information with ID numbers and consent forms that will include participant name and unique ID. These raw data files will be stored in separate secure locations (encrypted data file on a password-protected desktop within my locked office and locked file cabinets within my locked office). The master code list and all raw data files will be destroyed once all data collection is completed and analyzed.

Monitoring and Processes for Adverse Events.

We do not expect that participants will experience adverse events. Although unlikely, if during our research studies with family caregivers we observe neglect, abuse, or a situation that is otherwise dangerous for children, we would ethically have to report such an observation to a higher authority such as Child Protective Services. For any other adverse event, staff will inform the Principal Investigator who will also communicate the adverse event to the study Safety Officer and then appropriate services and authorities (e.g. police, medical services, UCLA Office of the Human Research Protection Program) and request assistance. In all instances of adverse events, an Adverse Events incident report will be written and submitted to the UCLA Office of the Human Research Protection Program by the Principal Investigator. In addition, the funding agency and appropriate authority/ies will also be informed by the Principal Investigator. All phases of the study will be reviewed by the UCLA Office of the Human Research Protection Program.

Analysis Plan

Data Analysis Aim 1

Focus groups will be professionally transcribed and translated. The PI and Co-Is, Drs. [name] and [name], will independently synthesize and organize the qualitative data into the *a priori* domains of acceptability and usability mentioned above, and identify any emergent themes. The PI and Co-Is will then meet to iteratively discuss and resolve differences by consensus. Focus groups will be used to analyze the following domains related to acceptability and usability: (1) identify preferred linguistic and culturally appropriate terms and images; (2) acceptability of sharing text, pictures, videos, and audio to support group learning; (3) preferred strategies for learning; (4) ease of using interactive texts; and (5) ease of completing interactive tasks.

Data Analysis Aim 2.

Acceptability and feasibility will be analyzed using scores on the adapted HRSA MCHB Family-Centered Care items and the implementation and evaluation framework measures. Feasibility indicators will be evaluated against *a priori* criteria from the literature,^{63,66,67} providing a roadmap to evaluate “success” and whether to move forward with an R01 randomized clinical trial. Analyses of data from measures of children’s weight-related behaviors and BMI, as well as care-giver data will be done using Stata 15.0 software. Means and frequencies of outcome variables will be done for both the intervention and control group. T-tests and chi-square tests will evaluate for group differences on baseline characteristics. Mixed effects linear regression models will be used to analyze the intervention’s effect on the outcomes of child behaviors and BMI score over time (baseline, 1- and 6-month post-baseline). These models will include intervention status, baseline dietary, physical activity, media-viewing behaviors, and BMI score, and selected covariates given the sample size. Furthermore, caregiver feeding practices and acculturation will be evaluated as potential moderators of intervention effects on child outcomes. Group Cohesion will be analyzed using scores on the adapted Physical Activity Group Environment Questionnaire⁶⁰ and analyzing participant shared content using Linguistic Inquiry and Word Count software and theme taxonomies as used in other online support group studies^{64,65} These variables, will be examined to evaluate the extent to which they function as potential mediators of child BMI outcomes.

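### The Aim 2 mixed model does not specify the 6-month effect it is meant to estimate; fitted with the terms listed, its intervention coefficient is a three-visit average that includes baseline

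*Combined protocol and SAP*

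**What the plan says.** The Analysis Plan (Data Analysis Aim 2) proposes mixed effects linear regression for the intervention's "effect on the outcomes of child behaviors and BMI score over time (baseline, 1- and 6-month post-baseline"). The next sentence gives the model terms: "These models will include intervention status, baseline dietary, physical activity, media-viewing behaviors, and BMI score, and selected covariates given the sample size". It names no visit term, intervention-by-visit term, visit-specific contrast or within-child covariance structure, and none appears elsewhere in the document.

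The Protocol Synopsis (Summary) sets the target. The pilot is to give preliminary effect sizes for "weight-related behaviors and BMI z-scores at 6 months post-intervention, in preparation for a larger randomized trial". Later in the same section the data are to be "collected at baseline, 1-month, and 6-months after the intervention begins in order to estimate preliminary effect sizes and standard deviations".

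Two other statements in Data Analysis Aim 2 bear on the consequence. Descriptive summaries are planned: "Means and frequencies of outcome variables will be done for both the intervention and control group". Feasibility indicators, judged against prior criteria, are what inform "whether to move forward with an R01 randomized clinical trial".

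**The concern.** Estimating effect sizes is a stated purpose of the pilot, with 6 months named as the time of interest, yet no model parameter is tied to that quantity. Taken at face value, the listed terms put the same measurement on both sides of the model and give one intervention coefficient for all visits. The baseline visit cannot carry an intervention effect, so including it as an outcome row pulls that coefficient away from the 6-month effect. The same model would also show a positive effect for an intervention that worked at 1 month and had faded by 6. Two competent analysts following this text could report different numbers as the effect size.

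**Working it through.** **Inputs from the documents.** There are 66 caregiver-child dyads, two randomised arms, visits at 0, 1 and 6 months, and the model terms quoted above. The documents give no effect size, SD, correlation, allocation ratio or power calculation, so there is no figure of the plan's own to reproduce.

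**Assumed for illustration.** 33 per arm, SD 1 at each visit, complete data unless stated, and d6 = 0.4. Correlations (baseline–1 month / baseline–6 months / 1–6 months) follow four patterns: A 0.5 throughout; B 0.9 throughout; C 0.8/0.5/0.5; D 0.95/0.8/0.82.

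**1. Terms as listed, random intercept.** With balanced data, the coefficient of a child-level term equals that from ordinary regression of each child's three-visit mean on arm and baseline. Once adjusted for itself, the baseline row contributes exactly zero. The coefficient therefore estimates (0 + d1 + d6)/3. Setting this equal to d6 gives d1 = 2 × d6.

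**2. Baseline row dropped, no interaction.** The coefficient estimates (d1 + d6)/2, which equals d6 only if d1 = d6.

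| d1 (d6 = 0.4) | As listed | Baseline row dropped |
|---|---|---|
| 0 | 0.13 | 0.20 |
| 0.2 | 0.20 | 0.30 |
| 0.4 | 0.27 | 0.40 |
| 0.8 | 0.40 | 0.60 |

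Simulation agrees with these values. With d1 = 0.5 and d6 = 0 (faded by 6 months), the listed terms still give 0.5/3 = 0.17. With d1 = 0.2, d6 = 0.4 and about 22% of 6-month values missing at random, they average 0.18–0.19. In the complete-data case with d1 = 0.2, the 95% CI covers 0.40 in 60% (A), 10–11% (B), 42–43% (C) and 11–12% (D) of runs.

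**3. Interaction added, baseline kept on both sides, random intercept.** The 6-month result is unbiased. Its SE depends on which quantity is reported.

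- *Arm plus interaction (the 6-month contrast).* The common baseline slope is b = (1 + r01 + r06)/3. The true variance factor is 1 + b² − 2b·r06. The model instead uses the average of the three visits' variances, including the small one at baseline, (1 − b)². For A, b = 0.667. The true SD is √(0.778 × 2/33) = 0.217. The model SE is √[(0.111 + 0.778 + 0.778)/3 × 2/33] = 0.184. Simulation gives the same two figures.
- *Interaction coefficient (difference in change).* The true SD is √[2(1 − r06) × 2/33]. The model SE replaces r06 by the mean of the three correlations.
- *For comparison, baseline-adjusted 6-month difference.* The SD is √[(1 − r06²) × 2/33].

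| Pattern | Arm plus interaction: model SE / true SD (coverage), simulated | Interaction coefficient: model SE / true SD | Baseline-adjusted SD |
|---|---|---|---|
| A | 0.184 / 0.217 (91%) | 0.246 / 0.246 | 0.213 |
| B | 0.089 / 0.106 (90%) | 0.110 / 0.110 | 0.107 |
| C | 0.159 / 0.225 (84%) | 0.220 / 0.246 | 0.213 |
| D | 0.098 / 0.152 (80%) | 0.132 / 0.156 | 0.148 |

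The interaction coefficient has a valid SE when correlations are equal (A, B). Its shortfall in C and D comes from the random-intercept covariance, not from using baseline twice. Its cost against baseline adjustment is clear at a baseline-to-6-month correlation of 0.5 (0.246 against 0.213) and slight at 0.9 (0.110 against 0.107).

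**4. Follow-up outcomes only, baseline as covariate, visit-specific effects.** This estimates d6. With unstructured covariance, simulated coverage is 94–96%.

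**5. Raw difference of 6-month means.** SE = √(2/33) = 0.246 in every pattern. It is valid but makes no use of baseline.

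**The case against.** The strongest reply is that the parenthesis with the three visits only records when data are collected, and that analysing outcomes over time is ordinary shorthand for visit-specific effects. With baseline as a covariate, this is the sound model in step 4, and nothing in the text excludes it. That stands as a possible reading. It does not remove the gap, because the plan does not say so and the words most directly describe something else. A reader should not conclude, however, that the trial will certainly use baseline on both sides.

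A reader might also infer that any model keeping baseline on both sides gives either a diluted estimate or too narrow an interval. That is not so. Once an interaction is added, its coefficient is unbiased, and under equal correlations its SE is correct; the main cost is precision.

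The numerical sizes rest wholly on assumed inputs, and the lowest coverage figures need both the as-listed reading and high correlations. That is fair: only the formulas follow from the listed terms, given a random intercept and complete data. Nor does the plan state a covariance structure that could be called wrong.

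Finally, the planned arm summaries already allow a raw 6-month comparison. That is true, but it is no more precise than √(2/33) allows and is not what the models are there to provide.

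**Conclusion.** The point holds as a gap in specification that should be fixed. The plan does not say which model quantity is the 6-month effect size. Under the terms as listed, with a random intercept and complete data, the intervention coefficient is (0 + d1 + d6)/3. With assumed d1 = 0.2 and d6 = 0.4, that is 0.20, half the intended quantity. The direction is not fixed: for positive effects the estimate is too small when d1 is below 2 × d6 and too large when it is above.

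The consequence is limited. A reader might infer that the decision to proceed, or the size of the later trial, is compromised. The documents do not support that: the effect sizes are described as preliminary, the decision is tied to feasibility indicators, and no rule carries the estimate into a sample size.

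The time point is also unsettled. The Summary refers to "BMI z-scores at 6 months post-intervention" in one place and counts 6 months from the start of the intervention in another, while the Analysis Plan counts from baseline.

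**What to change.** Use baseline once, in one of two ways:

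- (a) Model the 1- and 6-month outcomes only, with visit, intervention, intervention-by-visit, the same outcome's baseline value and baseline-by-visit.
- (b) Fit a constrained longitudinal model with baseline as an outcome, a baseline mean common to both arms and intervention-by-visit terms, and without the baseline covariate.

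Preferably state an unstructured within-child covariance, or robust SEs with a small-sample correction, because visits at 0, 1 and 6 months are unequally spaced. In the illustration, with d1 = 0.2, d6 = 0.4 and complete data, both models average 0.39–0.40 and cover 94–96% with unstructured covariance. With a random intercept alone, coverage falls to 91–92% in C and 88–90% in D.

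Name the between-arm difference at 6 months, with its 95% CI, as the effect size to report, and give the 1-month difference alongside it. Reconcile the two descriptions of the 6-month time point in the Summary, so that the effect is tied to one stated visit.

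The cost is one or two sentences in the plan and a few more model parameters. All variables and visits are already planned, so no new data are needed.

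### Does the analysis plan drop mediators that the synopsis promises to study?

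*Combined protocol and SAP*

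**What the plan says.** The Summary in the Protocol Synopsis states: "Mediators of the intervention will include measures of caregiver self-efficacy, caregiver feeding practices, and group support". It gives the measurement times once for the whole study: "intervention data will be collected at baseline, 1-month, and 6-months after the intervention begins". It does not assign instruments to visits.

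Data Analysis Aim 2, under Analysis Plan, is the only text on quantitative analysis. It mentions caregiver measures in four ways:

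- A general software statement covers child measures "as well as care-giver data will be done using Stata 15.0 software".
- A moderator statement says that "caregiver feeding practices and acculturation will be evaluated as potential moderators of intervention effects on child outcomes".
- Group cohesion is to be studied through a questionnaire score and by "analyzing participant shared content using Linguistic Inquiry and Word Count software".
- The next sentence reads: "These variables, will be examined to evaluate the extent to which they function as potential mediators of child BMI outcomes".

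Self-efficacy appears nowhere in that section. On the arms, the Summary describes booster "doses that incorporate behavioral change techniques using a group strategy" for the intervention, and "the comparison condition, in which caregivers receive usual WIC services".

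**The concern.** Read side by side, the two sections do not match, and three things stand out.

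First, self-efficacy is promised as a mediator and then disappears. The software statement gives it no role, model, visit or outcome.

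Second, feeding practices change role, from mediator in the Summary to moderator in Aim 2. The timing matters: a moderator should normally be a value from before randomisation, while a mediator must be measured after randomisation and before the outcome. Aim 2 gives no visit for either role.

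Third, the mediation sentence follows directly on group cohesion, part of which is assessed from what participants share by text. The documents describe no text group for the comparison arm. A measure that exists in one arm only cannot be contrasted between arms, and so cannot carry a mediated randomised effect.

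At stake would be the mechanism evidence taken into the later R01 proposal. Recruitment and Retention treats caregivers as the people through whom child behavior changes, and self-efficacy and feeding practices are the two named mediators that measure the caregiver and not the group.

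**Working it through.** The documents give no figure to reproduce here, so the check is a comparison of text, followed by one small calculation on the shared-content measure.

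| Variable | Summary | Aim 2, narrow reading | Aim 2, broad reading |
|---|---|---|---|
| Self-efficacy | mediator | not named | not named |
| Feeding practices | mediator | moderator only | moderator and mediator |
| Group support (taken to be group cohesion) | mediator | mediator | mediator |
| Acculturation | not listed | moderator only | moderator and mediator |

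In the narrow reading, the mediation sentence refers only to the group-cohesion measures just before it. In the broad reading it also takes in the variables of the preceding moderator sentence. Equating group support with group cohesion is an inference.

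**Count.** On the narrow reading, 3 − 1 = 2 of the 3 listed mediators have no named mediation analysis. On the broad reading it is 3 − 2 = 1, self-efficacy. The narrow reading is grammatically more natural. The broad one agrees better with the Summary on feeding practices, but it also makes acculturation a mediator, which the Summary does not list.

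**What the count measures.** It records which variables are named, not which have a specified analysis. Aim 2 gives no mediation model, visit or estimand for any variable, group cohesion included. Self-efficacy is thus one naming step behind group cohesion. It is not an unplanned variable beside a fully planned one.

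**Moderator timing.** One variable can be both moderator and mediator, so the two roles of feeding practices do not contradict each other. The three visits allow the usual arrangement of baseline values for moderation and 1-month values for mediation of a 6-month outcome, provided the instruments are given at those visits. A baseline moderator introduces no bias, and nothing states that a later value will be used.

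**Shared content.** Aim 2 presents it as one of two ways to study group cohesion, and does not say in which arms cohesion is scored. That it would be entered as a between-arm mediator is inferred. If it exists only in the intervention arm, it can yield only a within-arm association. Assuming 1:1 allocation (66 / 2 = 33) and a true correlation near 0, the 95% half-width is tanh(1.96 / √(33 − 3)) = 0.343. With about 20% attrition, also assumed (0.8 × 33 ≈ 26), it is tanh(1.96 / √(26 − 3)) = 0.387. Such a result is descriptive however it is labelled.

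**Effect on the main results.** The mixed models use intervention status, baseline values and selected covariates. None of the mediators is named as a term in them. The six acceptability and feasibility outcomes in the Summary do not depend on a mediation analysis.

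**The case for a change.** The strongest case for a change is that the omission of self-efficacy does not depend on how the mediation sentence is read. The variable does not occur earlier in Aim 2, so no pronoun can reach it. Roles and visits left open can be chosen after the data are seen, which weakens even exploratory evidence. The remedy is only a few sentences, with no new visits.

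The first part stands: Aim 2 does not name self-efficacy. It does not follow that the pilot would produce no indirect-effect estimate for it, because the Summary says it will be studied as a mediator and Aim 2 does not retract that.

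The point about post hoc choice is sound in general. Its weight here is small, since the Summary presents the mediation work as part of a pilot meant to give preliminary data, and no confirmatory claim is attached to it.

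The cheapness of the remedy is also less clear than it looks. It would be either to add analyses or to shorten the Summary's list, depending on whether both caregiver instruments are given at baseline and 1 month in both arms, which the documents do not show. A 1-month mediator would also miss the two months of boosters. The published text may be condensed: Aim 1 refers to domains mentioned above that are not listed earlier, and Aim 2 relies on framework measures it does not define. A fuller account may exist elsewhere, though that cannot be confirmed.

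**Conclusion.** The mismatch in naming is real, but no change to the plan follows. One of three mediators is unnamed in Data Analysis Aim 2 for certain. A second lacks a named mediation analysis only on the narrower reading. This is a gap of detail in secondary, exploratory work that an analyst would fill in the standard way: moderators at baseline, mediators after baseline, and any measure found in one arm only reported as an association within that arm. Nothing in the documents commits the team to anything else. The main mixed models and the six acceptability and feasibility outcomes are the same whichever reading is taken.

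This rests on three assumptions: that the Summary and the Analysis Plan are read as one document, that group support and group cohesion are the same construct, and that the caregiver measures the Summary lists are in fact collected. If the last were false, one sentence of the Summary would be inaccurate, still with no effect on the main results.

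### Shared-post content is planned as a mediator of child BMI, but only the intervention arm as described has a group to post in, so the analysis cannot show mediation; for the cohesion score the arm is not stated

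*Combined protocol and SAP*

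**What the plan says.** The Protocol Synopsis (Summary) describes an intervention of interactive texts and later booster messages that "incorporate behavioral change techniques using a group strategy". Dyads are randomised to this or to "the comparison condition, in which caregivers receive usual WIC services". No texting group, posting channel or attention control is described for the comparison arm. The synopsis lists "frequency of sharing/replying to texts by caregiver-type" among the acceptability and feasibility outcomes, and names group support as one of the mediators of the intervention. On timing, "data will be collected at baseline, 1-month, and 6-months after the intervention begins".

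The Analysis Plan (Data Analysis Aim 2) says "Group Cohesion will be analyzed using scores on the adapted Physical Activity Group Environment Questionnaire" and by "analyzing participant shared content using Linguistic Inquiry and Word Count software", together with theme coding. Both kinds of measure are then to be "examined to evaluate the extent to which they function as potential mediators of child BMI outcomes". The section names the arms for the outcome summaries ("Means and frequencies of outcome variables will be done for both the intervention and control group") but names none for the group measures. It gives no mediation model, no metric for the post content, and no rule for comparison dyads.

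**The concern.** To say that a variable mediates an intervention's effect, one needs an effect of arm on the variable and an effect of the variable on the outcome given arm. The first is a between-arm contrast. Post content exists only where there are posts, and as described only the intervention arm has a place to post. The contrast is then either undefined or fixed by the design.

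What is at stake is one kind of statement: that what caregivers shared in the group carried the intervention's effect on child BMI. The pilot is meant to supply preliminary data for an R01 proposal, and such a statement could be carried into it without support.

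**Working it through.** The plan gives no figure to reproduce here. The point is structural, so the check takes each way in which the planned analysis could be run.

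**Inputs from the documents.** 66 dyads; two randomised arms; the group strategy described only within the intervention; usual services in the comparison arm; shared content and cohesion both named as potential mediators of child BMI. **Assumed:** 33 dyads per arm (66 / 2), because the allocation ratio is not stated.

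Let A be the arm (1 = intervention, 0 = comparison), M the content measure and Y the BMI outcome. The usual decomposition is

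- M = a0 + a·A + error
- Y = b0 + c·A + b·M + error
- indirect effect = a × b

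**Case 1: M is a proportion or profile score** (share of words in a category, theme profile). With no posts, the denominator is zero and M is undefined in the comparison arm. Only the intervention arm enters, where A = 1 throughout. The first regression has 2 columns but rank 1, and the second has 3 columns but rank 2. Neither a nor c can be estimated, so a × b cannot be formed.

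**Case 2: M is a count** (posts per theme, words per category). A zero can be entered for every comparison dyad. Then

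- a = (intervention mean of M) − 0 = intervention mean of M. This is positive as soon as anyone posts, because comparison caregivers have nowhere to post.
- b: comparison dyads have no variation in M, and A absorbs their mean outcome. Without covariates, b is exactly the slope fitted in the intervention arm alone. With covariates, comparison dyads help to estimate the covariate coefficients and residual variance, but still supply no variation in M.
- a × b = (intervention mean of M) × (intervention-arm slope).

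The product can be computed, but its only uncertain link is a non-randomised association within one arm. Caregivers who post more may differ in motivation, time or literacy, and these may also bear on child BMI.

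**Case 3: the intervention arm is analysed alone.** The wording allows this. It estimates the same within-arm association and does not address whether the intervention worked through M.

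**Precision of the within-arm association.** For an observed correlation of r = 0.3 and n = 33, by Fisher's z:

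- atanh(0.3) = 0.310; half-width = 1.96 / √(33 − 3) = 0.358
- limits on the z scale: −0.048 and 0.667
- 95% CI for r: −0.05 to 0.58

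This is optimistic. It assumes no loss to follow-up and independent caregivers, whereas members of the same text group may resemble one another.

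**Cohesion score.** The questionnaire asks about a group, and the only study group described is in the intervention. That suggests intervention-arm collection, but the documents do not say who completes it or about which group. If one arm only, the score is undefined in the other arm, as in case 1. If both arms answer about a group that both have, a can be estimated and the objection falls away.

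**The case against.** The strongest reply is that the text is incomplete and not wrong. No mediation model is named, the language is hedged, and an intervention-arm analysis fits the words. The synopsis names group support, not shared content, among the mediators. This stands in part: the plan does not commit to a particular invalid model. But a mediator of an intervention ordinarily implies the full path from arm to outcome, and none of the three readings supports that conclusion for post content. The label needs to change, not just the detail.

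A second reply is that the metric is not given, and counts have a natural zero. This also stands in part. A reader might infer that no shared-content analysis can be computed at all. The documents do not support that, since counts per theme or category can be. The zero still does not rescue mediation, because the comparison value is set by the design.

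A third is that the mediator-outcome path is non-randomised for every mediator. True; what is specific here is that the arm-to-mediator path lacks a real comparison as well.

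A reader might also infer that the cohesion analysis is wrong. The documents support only that its arm and reference group are unstated.

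Lastly, the practical consequence is limited. The plan ties the decision to move to an R01 trial to feasibility indicators, not to mediation results.

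**Conclusion.** The concern holds for shared-post content. Under the design as described, proportion or profile scores give no estimable effect of arm on the mediator. Counts give one fixed by design, with the slope taken from the intervention arm alone. An intervention-arm analysis is a non-randomised association. None of these is evidence that shared content mediates the intervention's effect on child BMI. For the cohesion score, and for group support if it uses the same questionnaire, the plan is unspecified.

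Severity is minor. The analysis is exploratory, and feasibility results and arm-difference estimates are untouched. A reader might infer that the plan inflates false-positive findings or biases the comparison of arms; nothing in the documents shows either.

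The conclusion rests on the comparison arm having no posting channel, which is how the synopsis reads. It does not depend on sample size. The interval above rests on the assumed 33 independent caregivers and shows only that the within-arm association would be imprecise.

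**What to change.** Change the wording of Data Analysis Aim 2:

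1. Reclassify the shared-content measures as intervention-arm process measures, state the metric, and report them descriptively. This fits the synopsis, which already counts sharing and replying among the feasibility outcomes. Label any baseline-adjusted association with child BMI exploratory and non-causal. Give it as an estimate with a confidence interval that allows for group membership if caregivers are placed in text groups.
2. State in which arm or arms, and about which group, the cohesion questionnaire is completed. If only in the intervention arm, treat it as in item 1, and likewise group support if it uses that instrument. If it is collected in both arms about a group that both have, say so and keep it as an exploratory mediator.
3. Limit exploratory mediation analysis to variables measured in both arms (for example caregiver self-efficacy, if so collected), with the mediator measured before the outcome. A 1-month mediator with a 6-month outcome would serve. Note its limit: if the 2 months of boosters follow the 1 month of texts, contact runs to about month 3 (1 + 2), and a 1-month value may miss later change.

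The cost is analysis-plan text only, with no new data or participants. The sponsor gives up a mediation claim for shared content, and possibly for cohesion, that the described design cannot support.
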